Appendix A. Schedule of study assessments – Treatment Period

¹ All visits should take place at the end of the defined period (i.e. M7 visit should be scheduled at the end of Month 7, M8 visit should be scheduled at the end of Month 8, etc.). All visit dates should be calculated from the date of Day 1 visit (in the main study). A month is defined as 28 days/4 weeks. Visits should be scheduled ± 3 days (-3/+ 2 days for Month 7 visit) from the calculated date.

² All Month 6 assessments except informed consent and inclusion/exclusion criteria would have been performed as part of the main study (18-OBE2109-002 - Edelweiss 2).

³ ECG should be performed at about the same time but before the PK sample

 $^4~$ If endometrium thickness in TVUS is $\leq 5~$ mm, no endometrial biopsy will be necessary.

⁵ Overnight fasting is required.

 $^{6}\,$ Only for subjects who met the following criterion at any site on the M6 DXA scan: -2.5 < Z-score \leq -1.5

Schedule of study	assessments -	Treatment 1	Period ((cont'd)
e e e				· /

Schedule of study assessments – Treatment Period							
Timing ¹	Treatment Period						
	M6 ²	M7	M8	M9	M10	M11	M12
IMP accountability	X	X	X	X	X	X	X
Dispense linzagolix/placebo kit	X	X	x	x	x	X	
Dispense ABT/placebo kit	X			х			
EHP-30, EQ-5D-5L and PROMIS ³	x	x		x			x
mPGIS, PGIC, HRUQ and HRPQ ³	X	х	х	х	X	х	Х
SSIQ and PSIQ ³	x						X
Blood sample for PK ⁴	X	х	х	х	X	X	Х
E2, LH, P4	X	X	x	X	X	x	x
SHBG	X			x			X
Bone biomarkers	X			х			Х

¹ All visits should take place at the end of the defined period (i.e. M7 visit should be scheduled at the end of Month 7, M8 visit should be scheduled at the end of Month 8, etc.). All visit dates should be calculated from the date of Day 1 visit (in the main study). A month is defined as 28 days/4 weeks. Visits should be scheduled ± 3 days from the calculated date.

² All Month 6 assessments except informed consent and inclusion/exclusion criteria would have been performed as part of the main study.

³ ClinROs (PSIQ and HRUQ) will be administered to the subject by the site staff and the responses will be filled in the eDiary. ePROs (EHP-30, EQ-5D-5L, PROMIS, PGIS, PGIC, HRPQ and SSIQ) will be filled in by the subject in the eDiary.

⁴ PK samples should be taken after the ECG and before the daily dose of IMP.

Appendix B. Schedule of study assessments – Follow-up Period

Schedule of study assessments – Extension Follow-up Period								
Timing ¹	M1 ExFU	M3 ExFU	M6 ExFU					
Concomitant medication	X	x	X					
Adverse events	x	x	X					
Columbia-Suicide Severity Rating Scale	x	x	X					
ECG	x	x	X					
Physical examination (including weight)		x	X					
Vital signs	x	x	X					
Gynecological examination		x						
Manual breast examination		x						
Endometrium TVUS		x	X					
Endometrial biopsy	x ²	x ²	x ²					
Clinical laboratory & urinary protein dipstick	x	x ⁴						
Subject eDiary completion check	x	x	X					
Subject eDiary collection and deactivation			X					
EHP-30, EQ-5D-5L, PROMIS, HRUQ, HRPQ		x	X					
mPGIS and PPGIC	x	x	X					
BMD by DXA			x ⁵					
E2, LH, P4	x	x						
FSH at local laboratory for subjects that do not resume menses at M3 ExFU visit		x	I					
Bone biomarkers		x						
Permitted analgesic prescribing/dispensing	X	x						
Vitamin D and calcium dispensing	X	x						
Urine pregnancy test and contraceptive dispensing and counselling	X	X	x					

¹ All follow-up study visits should take place at the end of the defined period (i.e. M1 ExFU visit should be scheduled at the end of the first month of follow-up, M3 ExFU visit should be scheduled at the end of the third month of follow-up, etc.). A month is defined as 28 days/4 weeks. Visits should be scheduled ± 7 days from the calculated date.

² Endometrium biopsy will be taken only if diagnosis at preceding visit was different than "benign endometrium" or if no endometrial biopsy was done at M12 nor at any visit since M12.

³ An end-of-study biopsy is mandatory if no endometrium biopsy was obtained at M12 nor at any of the subsequent visits.

⁴ Overnight fasting is required.

⁵ Subjects with a BMD decrease from main study baseline of > 1.5% for lumbar spine and/or > 2.5% for total hip at M6 ExFU visit will have an additional DXA scan 6 months later.

Appendix C. Endometriosis Health Profile questionnaire (EHP-30)

Final English (US) EHP-30 + Section C

© Copyright, Oxford University Innovation Limited 2001. All Rights Reserved. The authors, being [name], [name] and [name], have asserted their moral rights.

PART 1: CORE QUESTIONNAIRE

DURING THE LAST 4 WEEKS, BECAUSE OF YOUR ENDOMETRIOSIS, HOW OFTEN HAVE YOU...

		Never	Rarely	Sometimes	Often	Always
1.	Been unable to go to social events because of the pain?					
2.	Been unable to do jobs around the house because of the pain?					
3.	Found it difficult to stand because of the pain?					
4.	Found it difficult to sit because of the pain?					
5.	Found it difficult to walk because of the pain?					
6.	Found it difficult to exercise or do the leisure activities you would like to do because of the pain?					

OBSEVA CONFIDENTIAL

DURING THE LAST 4 WEEKS,

BECAUSE OF YOUR ENDOMETRIOSIS, HOW OFTEN HAVE YOU...

		Never	Rarely	Sometimes	Often	Always
7.	Lost your appetite and/or been unable to eat because of the pain?					
8.	Been unable to sleep properly because of the pain?					
9.	Had to go to bed/lie down because of the pain?					
10.	Been unable to do the things you want because of the pain?					
11.	Felt unable to cope with the pain?					
12.	Generally felt unwell?					
13.	Felt frustrated because your symptoms are not getting better?					
14.	Felt frustrated because you are not able to control your symptoms?					

OBSEVA CONFIDENTIAL

DURING THE LAST 4 WEEKS,

BECAUSE OF YOUR ENDOMETRIOSIS, HOW OFTEN HAVE YOU...

		Never	Rarely	Sometimes	Often	Always
15.	Felt unable to forget your symptoms?					
16.	Felt as though your symptoms are ruling your life?					
17.	Felt your symptoms are taking away your life?					
18.	Felt depressed?					
19.	Felt weepy/tearful?					
20.	Felt miserable?					
21.	Had mood swings?					
22.	Felt bad-tempered or short-tempered?					

DURING THE LAST 4 WEEKS, SIG HOW OFTEN HAVE VO **BECAUSE OF VOUR END**

BECAUSE OF	YOUR ENDOMETRIOSIS, HOW OFTEN HAVE YO	U

		Never	Rarely	Sometimes	Often	Always
23.	Felt violent or aggressive?					
24.	Felt unable to tell others how you feel?					
25.	Felt others do not understand what you are going through?					
26.	Felt as though others think you are whining?					
27.	Felt alone?					
28.	Felt frustrated that you cannot always wear the clothes you would choose?					
29.	Felt your appearance has been affected?					
30.	Lacked confidence?					

19-OBE2109-005 PROTOCOL V2.0 DATED 24 AUGUST 2020

PART 2: MODULAR QUESTIONNAIRE CORRESPONDING TO SEXUAL RELATIONSHIPS

DURING THE LAST 4 WEEKS,

BECAUSE OF YOUR ENDOMETRIOSIS, HOW OFTEN HAVE YOU...

		Never	Rarely	Sometimes	Often	Always
1.	Experienced pain during or after intercourse? If not applicable, please check here					
2.	Felt worried about having intercourse because of the pain? If not applicable, please check here					
3.	Avoided intercourse because of the pain? If not applicable, please check here					
4.	Felt guilty about not wanting to have intercourse? If not applicable, please check here					
5.	Felt frustrated because you cannot enjoy intercourse? If not applicable, please check here					

Appendix D. PROMIS Fatigue – Short Form 6a

This scale is formally known as PROMIS Item Bank v1.0 – Fatigue – Short Form 6a. The questions and the response categories included in this scale are presented below.

Please respond to each question or statement by marking one box per row.

	During the past 7 days	Not at all	A little bit	Somewhat	Quite a bit	Very much
1	I feel fatigued					
2	I have trouble starting things because I am tired					
	In the past 7 days					
3	How run-down did you feel on average?					
4	How fatigued were you on average?					
5	How much were you bothered by your fatigue on average?					
6	To what degree did your fatigue interfere with your physical functioning?					

Scoring Rules:

The mapping of the response categories is as follows:

1 = Not at all; 2 = A little bit; 3 = Somewhat; 4 = Quite a bit; 5 = Very much

Assessment will be based on the sum of the individual scores across the six questions (possible scores 6 to 30, 6 =not at all, 30 =very much). Missing data will not be imputed.

Appendix E. Health-Related Productivity Questionnaire (HRPQ)

Health Related Productivity Questionnaire V2 (Generic)

	These questions deal with how illnesses and their treatment have affected your ability to remain in the workforce and perform work and daily activities in your home. Your responses and those of other patients will help us to understand the impact of illnesses and their treatment on these aspects of your life.					
1.	Currently emplo	nt employment status? oyed full-time —> Please go to Quest oyed part-time—> Please go to Quest nployed —> Please go to Quest	ion 2			
2.	How many hours were you scheduled to work at your job during the last week ? (If none or you are not employed, put a "0" here and go to Question 5.) Hours					
3.		ments keep you from working any of yo	ur scheduled hours during the last			
		sedb hours of work because of i reatments did not keep me from workir				
4.	For the hours that you did work during the past week, how did illnesses/treatments impact your work output?					
	Write a number	0%				
	on the line below, based on	Illnesses/treatments	Illnesses/treatments			
	this scale.	had no impact on how much I accomplished	kept me from accomplishing anything			
	% in	npact on work output				
5.	 How many hours of household chores (cooking, cleaning, gardening, repairs, etc.) did you plan to do during the last week? (If none, put a "0" here and go to Question 8.) 					
	Hours	1				
6.	Did illnesses/treat	ments keep you from doing any of your	planned hours of household chores			
	Yes → I workedb hours less because of illnesses/treatments. No, illnesses/treatments did not keep me from working my planned hours.					
7.	For the hours of household chores you did during the past week, how did illnesses/treatments impact your work output ?					
	Write a number	0%				
	on the line	Illnesses/treatments	Illnesses/treatments			
	below, based on this scale.	had no impact on how much I accomplished	kept me from accomplishing anything			
	% in	npact on work output				
	Health Related Productivity Questionnaire V2					
	All Rights Reserved					

OBSEVA CONFIDENTIAL

[This block of items deals with workforce participation and should be collected at study start]

- How long has it been since [X] developed?
 Months ______b Years
- 9. Which of the following statements are true of your life since [X] developed (mark all that apply):

[X] or its treatment(s) forced me to work part-time when I wanted to work full-time. For how long was this true? _____ Months ______ Years

- [X] or its treatment(s) kept me from having a job when I wanted to work full-time.
- For how long was this true? _____ Months ______ Years
- [X] or its treatment(s) kept me from having a job when I wanted to work part-time. For how long was this true? ______ Months ______ fYears

None of the above

Health Related Productivity Questionnaire V2 All Rights Reserved

OBSEVA CONFIDENTIAL

19-OBE2109-005 PROTOCOL V2.0 DATED 24 AUGUST 2020

Appendix F. Health Resource Utilization Questionnaire (HRUQ)

(To be completed by Site Staff)

Subject number: _____

Study Visit (please ensure to tick 1 visit only):

Treatment period	\Box Month 7	\Box Month 8	\Box Month 9	
	□ Month 10	□ Month 11	\Box Month 12	
Follow-up period	\Box Month 3 Ex	xFU □ Mo	nth 6 ExFU	

Date of Assessment:

Instructions to complete:

At each scheduled on-site visit in the Treatment Period (Month 6 through Month 12) and at Month 3 ExFU and Month 6 ExFU visits in the Follow-up period, please ask if the subject saw a **non-study** health care practitioner since her last scheduled on-site visit for a **routine/general health care visit that is not associated with an adverse event**.

Only record below the health care visits with non-study health care practitioners. Any visits associated with Adverse Events should be recorded on the AE eCRF form only (do not record below).

Question 1

Since the subject's last scheduled study on-site visit, has she seen a **non-study** health care practitioner (e.g., physician, nurse practitioner, physician assistant, dentist, physical therapist) for a **routine/general health care visit that is not associated with an adverse event?**

□ No □ Yes If Yes, please complete the questions 2 and 3 below.

Question 2

- a. Select the type of non-study health care practitioner who saw the subject.
- b. Indicate if it was at an office or a clinic (includes a hospital outpatient visit)
- c. Indicate the number of times the subject was seen by each practitioner.

Types of non-study health care practitioner who saw the subject	Type of facility		Number of t subject was	seen by
(check all that apply)			this non-stu care practiti	
	Office	Clinic	Office	Clinic
□ DENTIST				
FAMILY PHYSICIAN				
□ INFECTIOUS DISEASE SPECIALIST				

19-OBE2109-005 PROTOCOL V2.0 DATED 24 AUGUST 2020 Page 99 of 121			
INTERNAL MEDICINE SPECIALIST			
MEDICAL GENETICIST			
□ NURSE PRACTITIONER			
□ OCCUPATIONAL THERAPIST			
□ ORTHOPEDIC SURGEON			
PHYSICAL THERAPIST			
□ PLASTIC SURGEON			
REPRODUCTIVE ENDOCRINOLOGIST			
□ OTHER HEALTH CARE PRACTITIONER (specify type):			

Question 3

Did the Subject have any diagnostic or therapeutic procedures performed by a non-study health care practitioner since the last scheduled study on-site visit?

 \Box No \Box Yes If Yes, complete question 4 below.

Question 4

- a. Select the type of diagnosis/therapeutic procedures performed by non-study health care practitioner who saw the subject.
- b. Indicate the number of times the diagnosis/therapeutic procedures were performed.

Diagnostic/Therapeutic Procedure (check all that apply)	Number of times the procedure was performed
Ultrasound Scan	
Physical Examination	
Vital Signs	
MRI	
CT Scan	
X-Ray	
Biopsy and Histologic Examination	
Pelvic Exam	
Urine Test	
Blood Test	
Hysteroscopy	
SIS (Saline infusion Sonohysterography)	
Colposcopy	
Other (specify):	

Question 5

Has the patient spent any nights as a hospital in-patient since the last visit?

□ No □ Yes

If Yes, how many nights did they spend in hospital?

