- Change from baseline to each scheduled assessment in the number of pelvic pain-free days (assessed on the VRS) during the previous 4-week period
- Change from baseline to each scheduled assessment in ability to perform daily activities during the previous 4-week period, as assessed in the eDiary (daily function NRS)
- Change from baseline to each scheduled assessment in the number of days with no difficulty in doing daily activities due to EAP during the previous 4-week period as assessed in the eDiary (daily function NRS)
- Change from baseline to each scheduled assessment in the number of days when dyspareunia was a problem during the previous 4-week period (including days when sexual intercourse was avoided because of anticipation of pain) as assessed on the dyspareunia VRS
- Change from baseline to each scheduled assessment in the number of days when sexual intercourse was avoided because of anticipation of pain during the previous 4-week period as assessed on the dyspareunia VRS
- Change from baseline to each scheduled assessment in the number of days with uterine bleeding (including spotting) during the previous 4-week period measured by eDiary
- Change from baseline to each scheduled assessment in the number of days when school or work was missed due to EAP in the previous 4-week period as reported in the eDiary
- Change from baseline to each scheduled assessment in the number of days when the subject had to go to bed or lie down due to EAP in the previous 4-week period as reported in the eDiary
- Change from baseline to each scheduled assessment in the Pain, Control and powerlessness, Emotional well-being, Social support, Self-image dimensions and the Modular sexual relationship questionnaire of EHP-30 scores

19-OBE2109-005 PROTOCOL V2.0 DATED 24 AUGUST 2020

- Change from baseline to each scheduled assessment in the Health Related Productivity Questionnaire (HRPQ) scores
- Number of non-study endometriosis related health visits, number of days in hospital and type of procedures performed based on Health Resource Utilization Questionnaire (HRUQ) at each scheduled assessment
- Change from baseline to each scheduled assessment in the Physician/Subject Surgery Intention Question (PSIQ/SSIQ)
- Change from baseline to each scheduled assessment in the PROMIS Fatigue Short Form 6a
- Change from baseline to each scheduled assessment in the EuroQoL 5-Dimension 5-Level (EQ-5D-5L) questionnaire

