10.2.2 Post-treatment Follow-Up Period

Up to Month 6 Extension FU visit, the subject will continue to record on her eDiary, daily at approximately the same time each evening, her use of provided/prescribed analgesics, uterine bleeding, pelvic pain, dyspareunia, dyschezia and daily function.

The subject will be asked to bring her eDiary at each visit to the site during the entire Follow-Up Period.

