10.2.2.1 Study visit: Month 1 Extension FU (Month 1 ExFU)

Month 1 ExFU visit should be scheduled on Day 365 ± 7 days after main study Day 1 (or 28 days ± 7 days after last IMP intake for early discontinued subjects).

The following tests and evaluations will be performed at Month 1 ExFU visit:

- eDiary completion compliance check
- ePRO completion, ideally before any other procedures or assessments: mPGIS and PPGIC (must be completed last)
- Concomitant treatments recording
- AE recording
- Completion of the paper C-SSRS questionnaire (version for "already enrolled subjects" (see Appendix R) for patients responding to the C-SSRS for the first time during the study, or version "since last study visit" (see Appendix S) for patients for whom the C-SSRS was completed at the previous study visit)
- ECG
- Vital signs (BP and heart rate)
- Urine pregnancy test and contraception dispensing and counselling
- Urinary protein dipstick
- Blood samples for haematology, coagulation parameters, chemistry, hormones (E2, LH and P4)
- Endometrial biopsy only if diagnosis at Month 12 was different than "benign endometrium" or if no endometrial biopsy was done at Month 12 (see section 10.4.5).
- Prescribe/dispense permitted analgesics as rescue medication
- Dispense calcium and vitamin D supplementation

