10.2.2.2 Study visit: Month 3 Extension FU (Month 3 ExFU)

Month 3 ExFU visit should be scheduled on Day 421 ± 7 days after Day 1 (or 84 days ± 7 days after last IMP intake for early discontinued subjects).

The following tests and evaluations will be performed at Month 3 ExFU Visit:

- eDiary completion compliance check
- ePRO and ClinRO completion, ideally before any other procedures or assessments: EHP-30, EQ-5D-5L, PROMIS, mPGIS, PPGIC, HRUQ, HRPQ (mPGIS and PPGIC must be completed last)
- Concomitant treatments recording
- AE recording
- Completion of the paper C-SSRS questionnaire (version for "already enrolled subjects" (see Appendix R) for patients responding to the C-SSRS for the first time during the study, or version "since last study visit" (see Appendix S) for patients for whom the C-SSRS was completed at the previous study visit)
- ECG
- Physical examination, including weight recording
- Vital signs (BP and heart rate)
- Urine pregnancy test and contraception counselling
- Gynecological examination
- Manual breast examination (by palpation)
- TVUS of uterus
- Urinary protein dipstick
- Fasting (overnight) blood samples for haematology, coagulation parameters, chemistry, lipids, hormones (E2, LH and P4) and bone markers. For subjects who do not resume menses by the Month 3 ExFU visit, an FSH test should be performed at a local laboratory and the subject should be advised to consult for gynaecological evaluation.
- Endometrial biopsy only if diagnosis at preceding biopsy was different than "benign endometrium" or if no endometrial biopsy was done at Month 12 nor at any visit after Month 12 (see section 10.4.5).
- Prescribe/dispense permitted analgesics as rescue medication
- Dispense calcium and vitamin D supplementation

10.2.2.3 Study visit: Month 6 Extension FU (Month 6 ExFU) – End of Follow-up visit

Month 6 ExFU visit should be scheduled on Day 505 ± 7 days after Day 1 (or 168 days ± 7 days after last IMP intake for early discontinued subjects).

The following evaluations and tests will be performed at Month 6 ExFU Visit:

- eDiary completion compliance check
- ePRO and ClinRO completion, ideally before any other procedures or assessments: EHP-30, EQ-5D-5L, PROMIS, mPGIS, PPGIC, HRUQ, HRPQ (mPGIS and PPGIC must be completed last)
- Collection and deactivation of eDiary
- Concomitant treatments recording
- AE recording

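### In follow-up the HRUQ looks back only to Month 1 ExFU, a visit at which it is not given, so non-AE care in the first 28 days off drug is asked about at no visit

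*Protocol*

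**What the plan says.** **When the form is given.** Protocol Appendix F instructs site staff to ask "At each scheduled on-site visit in the Treatment Period (Month 6 through Month 12) and at Month 3 ExFU and Month 6 ExFU visits". Its tick boxes offer no Month 1 ExFU. Section 10.2.2.1 lists the questionnaires at Month 1 ExFU as "ePRO completion, ideally before any other procedures or assessments: mPGIS and PPGIC (must be completed last"; the HRUQ is absent. Section 10.2.2.2 includes it at Month 3 ExFU. In Appendix B the row "EHP-30, EQ-5D-5L, PROMIS, HRUQ, HRPQ" is marked at Month 3 and Month 6 ExFU only, and SAP Table 2 repeats this.

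**What it asks.** Question 1 begins "Since the subject's last scheduled study on-site visit, has she seen a" non-study practitioner. Question 3 (procedures) uses the same anchor. Question 5 reads "Has the patient spent any nights as a hospital in-patient since the last visit".

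**Whether Month 1 ExFU counts as a visit.** Section 10.2 schedules it at Day 365. Section 10.2.2 treats follow-up contacts as site attendances ("The subject will be asked to bring her eDiary at each visit to the site during the entire Follow-Up Period"), and Section 10.2.2.1 includes an ECG, vital signs and blood samples.

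**How the data are used.** Section 7.1.2 has the endpoint "Number of non-study endometriosis related health visits, number of days in hospital and type of procedures performed", taken from the HRUQ at every scheduled assessment. Section 6.1.2 words the matching objective for the Treatment Period. SAP Sections 2.5.1, 4.6 and 5 drop the efficacy analyses, and HRUQ data appear in Listings 16.2.6.6 to 16.2.6.8.

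**The concern.** A utilization form covers continuous time only if each recall period starts where the previous form stopped. During treatment this holds, because the HRUQ is given at every monthly visit. In follow-up it fails: Month 1 ExFU resets the look-back without the form being completed there.

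The omission is the same in the protocol text, the schedule, the form and the SAP table, so it is a mismatch between recall wording and schedule and not a slip in one table. The last dose is taken the day before the Month 12 visit (Section 10.2.1), so the missing interval is the first month off drug. A reader of a listing ordered over time could take a negative answer at Month 3 ExFU to mean no care since Month 12, which was not the question asked.

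**Working it through.** **Inputs.** Visit days and the follow-up window of ±7 days: Protocol Section 10.2. Month 12 window of ±3 days: Section 10.2.1.5. One month is 28 days. Recall anchors: Appendix F.

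**1. Reproduce the visit days.** Month 12 = 1 + 12 × 28 = 337. The ExFU visits are 337 + 28 = 365, 337 + 84 = 421 and 337 + 168 = 505. All match Section 10.2.

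**2. Lay out the recall periods.**

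| Visit | Day | HRUQ given | Recall starts | Days covered |
|---|---|---|---|---|
| Month 12 | 337 | yes | Month 11, Day 309 | 28 |
| Month 1 ExFU | 365 | no | – | 0 |
| Month 3 ExFU | 421 | yes | Month 1 ExFU, Day 365 | 56 |
| Month 6 ExFU | 505 | yes | Month 3 ExFU, Day 421 | 84 |

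Follow-up lasts 505 − 337 = 168 days. Covered: 56 + 84 = 140. Uncovered: 168 − 140 = 28, and 28/168 = 16.7%. Between Month 12 and Month 3 ExFU, 56 of 84 days are covered (66.7%).

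**3. Apply the visit windows.** Month 12 can fall on Days 334 to 340, Month 1 ExFU on Days 358 to 372 and Month 6 ExFU on Days 498 to 512.
- Shortest gap: 358 − 340 = 18 days. Smallest share: 18/(512 − 340) = 18/172 = 10.5%.
- Longest gap: 372 − 334 = 38 days. Largest share: 38/(498 − 334) = 38/164 = 23.2%.

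The same structure applies after early withdrawal. The withdrawal visit follows Month 12 procedures (Section 10.7.2), and Month 1 ExFU is then timed from the last dose.

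**4. Under-count.** The documents give no utilization rate. Assume the rate in the first 28 days is k times the later rate. The share of HRUQ-eligible follow-up use that is missed is 28k/(28k + 140).

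| k (assumed) | Share missed |
|---|---|
| 0.5 | 14/154 = 9.1% |
| 1 | 28/168 = 16.7% |
| 2 | 56/196 = 28.6% |
| 3 | 84/224 = 37.5% |

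**5. Is the interval recorded elsewhere?** Partly. Appendix F sends AE-related visits to the AE form. AEs are recorded up to Month 6 ExFU (Section 12.5) and SAEs are reported to the end of follow-up (Section 12.3.2). But Section 12.1.4 keeps usual worsening of endometriosis off the AE form, and Section 12.3.1 does not count admissions for elective surgery or normal disease management as SAEs. Non-AE care in the gap has no dedicated record.

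**6. After re-anchoring.** Recall at Month 3 ExFU becomes 421 − 337 = 84 days. Coverage is 84 + 84 = 168 of 168 days.

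**The case against.** The strongest reply is that little depends on this, and most of that stands.

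- **Use of the data.** The SAP plans no efficacy analysis, so no follow-up total will be produced. Even before early termination, Protocol Sections 13.1 and 13.5.2 planned only descriptive summaries by treatment group and time point.
- **Objective.** Section 6.1.2 is worded for the Treatment Period, where recall is contiguous. The endpoint in Section 7.1.2 does reach into follow-up, but only descriptively.
- **AE-related care.** It is recorded through AE and SAE reporting, as events and not as HRUQ counts. A reader who infers that all visits and admissions in the first month are lost goes too far.
- **Remote visits.** Section 5.7 allows remote visits during the pandemic. If Month 1 ExFU was remote, the last on-site visit for Questions 1 and 3 could be Month 12, and the gap would close for those items. Question 5 refers to any last visit and would not change.
- **The fielded form.** The HRUQ cleaning rules in SAP Section 4.2.8.2 cite items up to 9, whereas Appendix F numbers five questions. The device wording may differ from the appendix and cannot be seen here.

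A reader might also infer that unequal recall (28 days at a treatment visit, 56 and 84 in follow-up) makes care off drug look two or three times as frequent as care on drug. The documents do not support this as a bias: neither plans an on-drug versus off-drug comparison, and groups summarised at the same visit share the same nominal interval.

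None of this removes the gap when Month 1 ExFU is held on site as scheduled.

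**Conclusion.** The gap is real and follows from the plan as written. Non-AE health-care use in Days 337 to 365 is asked about at no visit: nominally 28 of 168 follow-up days (16.7%), with 18 to 38 days possible within the windows. This assumes that Month 1 ExFU takes place on site and that the fielded form uses the Appendix F wording.

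The resulting under-count cannot be sized from the documents. The 16.7% figure for missed use assumes a constant rate, and the range in the working shows how far it moves if the first month differs. The effect is confined to the follow-up part of one descriptive secondary endpoint that is now only listed. The Treatment Period objective is untouched. Low priority.

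**What to change.** **Form.** In Protocol Appendix F, and in the matching items of the eDiary version, anchor Questions 1, 3 and 5 to the visit at which the HRUQ was last completed. At Month 3 ExFU that is Month 12 or the withdrawal visit. This also makes the look-back independent of whether Month 1 ExFU was on site or remote.

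**Cost.** No added visit or questionnaire. Recall at Month 3 ExFU lengthens from 56 to 84 days, a length already accepted at Month 6 ExFU, and the device text must be updated.

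**Data already collected.** Rewording cannot recover the unasked days. Footnote Listings 16.2.6.6 to 16.2.6.8 with the uncovered interval and the recall length at each visit. Rescaling to a common interval is unnecessary, because no planned table would use it.
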